## 9 ANCILLARY LABORATORY RESEARCH STUDIES

### 9.1 Collection of samples

During the course of participating on this study, additional blood samples will be collected – 3 X 5 cc (SST tubes) and 3 X 3 cc (3.2% sodium citrate tubes).

9.2 Intended use: The following laboratory research studies will be done and will be correlated with the presence or absence of response.

- Quantification of microvesicles at different time points of AML treatment - during remission IC and while on eltrombopag
- Analysis of micro RNA (miRNA) in the microvesicles from different time points of AML treatment - during remission IC and while on eltrombopag.

The different time points of assessment are as follows:

- 1) At the time of diagnosis of AML but prior to initiation of remission IC
- 2) At the time of day 14 bone marrow assessment (range, 14-17) following remission IC
- 3) On day 3 (+/- 1 business day) of study drug treatment.
- 4) On day 6 (+/- 1 business day) of study drug treatment.
- 5) At the time of bone marrow biopsy to confirm CR (usually between days 30-45 of remission IC)

9.3 Tracking: Samples will be ordered and tracked using Clinical Trial Draw – Specimen Processing Requisition Form which will accompany the specimen. Samples will not be sent outside CCF.

9.4 Storage: Research samples will be stored with identifiers in the secure laboratory of the co-investigator, [name].

9.5 End of study procedures: Samples from consenting subjects will be stored until they are no longer of scientific value or if a subject withdraws consent for their continued use, at which time they will be destroyed.

9.6 Loss or destruction of samples: Should we become aware that a major breech in our plan for tracking and storage of samples has occurred, the IRB will be notified.

## 10.0 STUDY ENDPOINTS

### 10.1.1 Primary endpoint

The proportion of patients achieving a platelet count of  $\geq 50,000/\mu\text{L}$  by day 24 of IC on eltrombopag therapy. The treatment response parameters for platelet count recovery for this trial was derived from a cohort of 200 older AML patients (excluding acute promyelocytic leukemia and acute megakaryocytic leukemia) who underwent aggressive 7 + 3 cytarabine-based remission IC at the Cleveland Clinic between 2000 and 2011. The total CR rate in our historical cohort was 41%.

The median time to CR (defined as the time from the start date of IC to the achieving CR per

IWG criteria) was 34 days (range, 14-66). The median time to reach platelet counts  $> 50,000/\mu\text{L}$  was 24 days (range, 17-57) from the start date of IC.

### 10.1.2 Response to Eltrombopag

**Complete Response to eltrombopag** will be defined as improvement in platelet count (independent of platelet transfusions) to  $\geq 100,000/\mu\text{L}$  with eltrombopag that lasts for at least 4 weeks after discontinuation of eltrombopag. The date of achieving complete response to eltrombopag was defined as the first day of the four-week period with platelet count greater than  $100,000/\mu\text{L}$  off eltrombopag and independent of platelet transfusions. If the patient with platelet counts  $\geq 100,000/\mu\text{L}$  transition to subsequent post-remission therapy within the 4-week timeframe of eltrombopag discontinuation, then that will be considered a complete response.

**Partial Response to eltrombopag** will be defined as any improvement in platelet count to  $\geq 50,000/\mu\text{L}$  but less than  $100,000/\mu\text{L}$  despite use of the highest dose of eltrombopag for the entire duration of the study or drop in platelet counts to  $< 100,000$  after achieving complete response (necessitating resumption of eltrombopag treatment).

**No response (NR) is defined as failure to fulfill the above criteria for either complete response or partial response after 8 weeks of eltrombopag therapy and despite use of maximal escalated dose of eltrombopag.**

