## 7.0. TREATMENT PLAN

### 7.1. Eltrombopag Administration

Consecutive eligible patients will receive eltrombopag at an initial oral dose of 200 mg once daily. For patients of East-Asian heritage (Japanese, Chinese, Thai, Taiwanese and Korean), the starting dose will be 100 mg orally once a day.

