### 7.2. Dose Rationale

Eltrombopag 200 mg once daily has been selected as the starting dose for this study (100 mg for subjects of East Asian heritage). The maximum dose of study medication is 300 mg once daily (150 mg in subjects of East Asian heritage). The rationale for allowing dose titration up to 300 mg once daily is based on the following considerations:

- The effective dose for eltrombopag for AML patients with chemotherapy-induced thrombocytopenia is unknown, and 300 mg is the maximum dose that is currently being considered in the eltrombopag clinical program, as described in the CIB.(11)
- In a placebo-controlled Phase II study (NCT00102726) in 183 cancer patients receiving carboplatin and paclitaxel, eltrombopag was dosed at 50 mg, 75 mg and 100 mg with placebo as control arm in 1:1:1:1 ratio ) for 10 days after carboplatin and paclitaxel administration for up to 8 cycles. Eltrombopag was generally well tolerated as described in the CIB. (11). The study results for the 100 mg group demonstrated that there was evidence for increased platelet production in all three treatment arms after the nadir, with a gradual rise in platelet counts from Day 8 to 18 of chemotherapy. No apparent safety issues at 100 mg were identified.(28)
- In a Phase II, non-randomized, open label pilot study of eltrombopag in aplastic anemia patients treated with immunosuppressive therapy and with refractory thrombocytopenia (NCT00922883), no observed toxicities were reported in this study to date with intrasubject dose escalation of eltrombopag starting at 50 mg and going up to 150 mg.(29) The higher dose was continued in an extension phase. Improvements of both platelet and erythrocyte values have been observed following eltrombopag exposure in these patients.
- In ITP subjects, a dose exposure and response relationship has been seen for eltrombopag doses of 30 mg to 75 mg once daily. There was no significant difference between the safety profile of ITP subjects receiving 30, 50 or 75 mg of eltrombopag when administered for up to 6 weeks.
- In HCV subjects, a dose, exposure and response relationship has been seen for eltrombopag doses of 30 mg to 75 mg once daily, with geometric mean AUC (0- $\tau$ )

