### 7.3 Dose Adjustments for Eltrombopag

If after 2 weeks, the platelet count fails to reach 50,000/ $\mu$  L or above, the dose will be increased to 300 mg orally daily (150 mg orally daily for East-Asians). Depending on tolerability, dose modification will be individualized based on the patient's platelet count response according to the following rules:

Dose Modification / Adjustment of Eltrombopag	
If platelet count is $\leq$ 50,000/ $\mu$ L after 2 weeks of treatment with starting dose of eltrombopag*	Increase daily dose to 150 mg for East-Asians and 300 mg for all other ethnicities
If platelet counts are between 50,000 and $<$ 100,000/ $\mu$ L (untransfused) on the starting or escalated dose of eltrombopag	Continue on the same dose
If platelet counts reach $\geq$ 100,000/ $\mu$ L (untransfused) on the starting or escalated dose of eltrombopag at any time on study	Discontinue eltrombopag

\* Starting dose will be 100 mg for East-Asians and 200 mg for other ethnicities.

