## 7.7 Duration of Therapy and Off Study Criteria

Depending on tolerability, eltrombopag can be administered to all assigned study subjects for a total duration of 4 weeks (counted from the first day of eltrombopag administration) unless they meet one of the following criteria for removal from the study:

1. Withdrawal of consent. The patient's desire to withdraw from the study may occur at any time. The investigator should carefully consider whether the patient's withdrawal of consent is due to an adverse event, and if so, record the adverse event as the reason for withdrawal.
2. Violation of the study protocol, including a patient's failure to return for required treatments or assessments or failure on the part of participants with reproductive potential to practice effective birth control or non-compliance.
3. At the treating physician's clinical discretion, if any specific medical or psychosocial changes in patient's condition makes them unacceptable to further participate in the study.
4. If bone marrow biopsy performed to establish remission status (around day 30-45 of remission IC), confirm refractory or persistent disease or if there is leukemic involvement of extramedullary site (biopsy confirmation of skin or organ lesions, central nervous system involvement confirmed either by cerebrospinal fluid analysis or radiological exams) at any time during study.
5. Adverse events, including intolerance of eltrombopag not resolved by dose reduction, life threatening acute hypersensitivity reaction, persistent hepatotoxicity (refer to section 7.4.2), thrombosis/embolism (DVT, PE, stroke, TIA, myocardial infarction) other than central line thrombosis (refer to section 7.5.1) or evidence of disease progression on treatment (myeloid sarcomas). Participants who are removed from the study due to adverse events will be treated and followed according to established medical practice. All pertinent information concerning the outcome of such treatment will be entered in the CRF.

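### The first partial-response branch in 10.1.2 requires the highest dose throughout the study, which no patient dosed under 7.1-7.3 and 7.7 can receive

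*Combined protocol and SAP*

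**What the plan says.** Section 10.1.2 defines three categories of response to eltrombopag. Complete response needs a transfusion-independent count of at least 100,000/µL that is kept after the drug is stopped. The first branch of partial response needs a rise to at least 50,000 but below 100,000/µL "despite use of the highest dose of eltrombopag for the entire duration of the study". A second branch, for patients who fall back after a complete response, is a separate matter.

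The dosing rules are elsewhere:

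- **Start (7.1).** "Consecutive eligible patients will receive eltrombopag at an initial oral dose of 200 mg once daily"; for patients of East Asian heritage, "the starting dose will be 100 mg orally once a day".
- **Maximum (5.2, 7.2).** 300 mg once daily, or 150 mg for patients of East Asian heritage.
- **Escalation (7.3).** The rule begins "If after 2 weeks, the platelet count fails to reach" 50,000/µL, and then moves the patient to the maximum.
- **Counts from 50,000 to below 100,000/µL (7.3).** "Continue on the same dose", whether that is the starting or the escalated dose.
- **Duration (7.7).** Treatment can run for 4 weeks from the first dose.

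**The concern.** The response definition and the dosing rules describe different patients. The definition treats partial response as incomplete recovery under full dosing from beginning to end. The dosing rules give nobody full dosing from the beginning, and they withhold escalation from the patients whose counts lie in the partial-response range.

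Applied as written, the branch is empty. Applied loosely, it favors later recovery: a patient who needed escalation can qualify, and one who reached the same counts earlier on less drug cannot. Either way someone has to decide after the data are seen how these patients are labelled. In a trial of at most 31 patients, a few such decisions could move any comparison built on the labels.

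**Working it through.** The plan states no figure for this point, so the check follows the dose paths that the protocol allows.

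**Inputs.** Treatment lasts 4 weeks = 28 days (7.7). The earliest escalation is after 2 weeks = 14 days (7.3). Starting and maximum doses are 200 and 300 mg, or 100 and 150 mg for patients of East Asian heritage (7.1, 7.2).

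**Step 1: the most time possible at the highest dose.** 28 − 14 = 14 days, and 14/28 = 50%.

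**Step 2: the permitted paths.**

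| Count at 2 weeks | Days 1-14 | Days 15-28 | Days at highest dose |
|---|---|---|---|
| 50,000/µL not reached | starting dose | highest dose | at most 14 of 28 |
| 50,000 to below 100,000/µL, and staying there | starting dose | starting dose | 0 of 28 |

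The result is the same for 200/300 mg and 100/150 mg. A count of 100,000/µL or more stops the drug (7.3), and a restart after a liver-enzyme hold is at the starting dose (7.4.2). Both can only shorten time at the highest dose. No path gives 28 of 28 days, so none satisfies the branch.

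**Step 3: a longer duration does not help.** The no-response definition in 10.1.2 mentions 8 weeks of therapy. Over 56 days the limit would be 56 − 14 = 42 days, or 75%, which is still not the whole period.

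**Step 4: the loose reading.** Suppose the phrase means that the highest dose, once reached, is kept to the end. Two constructed patients show the effect:

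- A has 70,000/µL by drug day 8, stays on the starting dose as 7.3 requires, and levels off at 85,000/µL. A never receives the highest dose and does not qualify.
- B has 30,000/µL at 2 weeks, is escalated, and has 70,000/µL at week 4. B qualifies.

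A recovered sooner, to a higher count, on less drug.

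**Step 5: the starting-dose path is a main one.** Under 4.1 the drug follows the day 14-17 marrow, so escalation cannot come before about induction day 14 + 14 = 28. That is after the day-24 landmark, so recoveries by day 24 occur on the starting dose. At the rates in section 12 they number 31 × 0.60 = 18.6 to 31 × 0.80 = 24.8, about 19 to 25 of 31. This counts patients who reach 50,000/µL before escalation is possible. It does not count patients misclassified, because many may go on to 100,000/µL.

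**The case against.** The best defense is that the wording is loose and the category is not truly empty. The partial-response sentence speaks of the highest dose, while the no-response sentence speaks of a maximal escalated dose. The first could therefore mean the highest dose that this patient was assigned under 7.3, and then both A and B qualify. This is possible but strained: 5.2 and 7.2 fix a study maximum, and nothing in 10.1.2 makes the term relative to the patient. If that meaning was intended, the sentence still has to be rewritten to say so.

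Other parts of the defense stand:

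- Recoveries to 50,000/µL are reported regardless of label, through the primary endpoint and the times to 50,000 and 100,000/µL in 10.2 item 1.
- Neither 9.2 nor 10.2 item 4 cites 10.1.2. Section 2 has no objective framed in these categories, and section 12 gives them no analysis. Their use downstream is an inference.

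A reader might also infer that a countable group of patients is left with no category at all. The documents do not support this. They give no rate of plateau between 50,000 and 100,000/µL, so any count would rest on an assumed rate and the true number could be near zero. Having no category also depends on the 8-week condition for no response, a separate problem. With a workable no-response rule, these patients would be misclassified rather than uncategorized.

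**Conclusion.** The point holds. As written, none of up to 31 patients treated per protocol can be a partial responder through the first branch, because the highest dose is available for at most about 14 of 28 days. On the more natural loose reading, the branch includes escalated, slower responders and excludes patients who settle between 50,000 and 100,000/µL on the starting dose. This conclusion rests only on 7.1-7.3, 7.7 and 10.1.2, with no assumed rate.

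The effect is limited. The number misclassified cannot be derived from the documents. The primary endpoint, at least 50,000/µL by day 24, and the 21-of-31 decision rule do not use this definition. The characterization by AML subtype, etiology and cytogenetic risk (10.2 item 4) and the microvesicle and microRNA correlates (9.2) are affected only if they use the 10.1.2 categories. That seems likely, since 10.1.2 is where response to eltrombopag is defined. The definition should be corrected before those analyses, but it does not threaten the trial's main conclusion.

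**What to change.** Reconcile 10.1.2 with 7.3 and 7.7 by changing the analysis definition only:

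- Remove the dose condition from the first partial-response branch.
- Define partial response as a best transfusion-independent platelet count of at least 50,000 but below 100,000/µL during the protocol treatment period, at whatever dose 7.3 assigned. Transfusion independence must be stated, as it is for complete response; otherwise a post-transfusion count could qualify.
- Tabulate dose at response separately, so that recovery on the starting and the escalated dose can still be told apart.
- State in 9.2 and 10.2 item 4 whether the 10.1.2 categories are the ones meant.

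Make this edit together with the other corrections to 10.1.2. On its own it does not repair the 8-week no-response rule, nor does it place a patient who reaches 100,000/µL and falls back within 4 weeks without resuming the drug. The cost is a short rewrite of one definition and two cross-references. Dosing and data collection do not change.

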### **8.4 Long-term Follow-up**

All participants, regardless of reason for discontinuation, will be followed for survival and for AML transformation (an increase of blasts to a level  $\geq 20\%$  in peripheral blood or bone marrow) for five years from study registration as part of standard of care for CCF leukemia patients.

The following study calendar will be used:

	Pre- induction	Week 1	Week 2	Week 3	Week 4	Week 5	Week 6
						Inpatient/Outpatient	
Induction chemotherapy (IC)							
Study Medicationa							
Informed Consent	X						
Demographicsb	X						
Disease Characteristicsc	X						
Transfusion Historyd	X	X	X	X	X	X	X
Review of concurrent medications	X	X	X	X	X	X	X
Physical Examinatione	X	X	X	X	X	X	X
CSBEf	X	X	X	X	X	X	X
Performance statusg	X						
Hematologyh	X	X	X	X	X	X	X
Serum Biochemistryi	X	X	X	X	X	X	X
Chest x-ray	X						
Peripheral Blood Smearj	X					X	
Bone marrow biopsyk	X		D14 - 17			X	
Ophthalmology examl	X						
12 lead ECG	X			X m			
Adverse event monitoringn				X	X	X	X

Pre-induction assessment refers to evaluation at the time of diagnosis of AML prior to start of remission induction chemotherapy. Weeks as enumerated in the table refer to the time from the start date (day 1) of remission induction chemotherapy.

Week 1 is the week when the patient receives the standard 7+ 3 (cytarabine and anthracycline) remission induction chemotherapy

a. **Study Medication:** Eltrombopag dose as assigned. The drug will be started within 5 business days from the date of day 14 bone marrow biopsy if the day 14 bone marrow biopsy (range, 14-17) shows no morphological evidence of leukemia and will be continued for a total of 4 weeks unless discontinued earlier for reasons stated in the protocol.

b. **Demographics:** Date of birth, race, ethnicity, and gender.

c. **Disease Characteristics:** Date of AML diagnosis, AML category as classified by WHO, primary vs. secondary AML, type of secondary AML (antecedent hematologic disorder, therapy-related including prior radiation therapy and or cytotoxic chemotherapy for any condition).

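### Section 10.1.2 requires 8 weeks of eltrombopag before 'no response' can be scored, but treatment is capped at 4 weeks, so no patient treated per protocol can be a non-responder, and changing 8 to 4 alone does not repair the scale

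*Combined protocol and SAP*

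**What the plan says.** Section 10.1.2 grades platelet response to the drug in three categories.

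- *Complete response*: an untransfused count of at least 100,000/µL that lasts 4 weeks after eltrombopag is stopped. Moving on to post-remission therapy within those 4 weeks, with the count still at that level, also qualifies.
- *Partial response*, two routes: a rise to 50,000 to <100,000/µL "despite use of the highest dose of eltrombopag for the entire duration of the study"; or a fall below 100,000/µL after complete response, with the parenthesis "necessitating resumption of eltrombopag treatment".
- *No response*: neither of these "after 8 weeks of eltrombopag therapy and despite use of maximal escalated dose of eltrombopag".

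The treatment sections describe a shorter course with a stepped dose. Section 7.7 states that "eltrombopag can be administered to all assigned study subjects for a total duration of 4 weeks", counted from the first day of drug. Note a to the study calendar in section 8.4 says the drug "will be continued for a total of 4 weeks unless discontinued earlier for reasons stated in the protocol". Section 7.1 gives the start: "Consecutive eligible patients will receive eltrombopag at an initial oral dose of 200 mg once daily". Section 7.2 gives the ceiling: "The maximum dose of study medication is 300 mg once daily". Patients of East Asian heritage start at 100 mg, with a ceiling of 150 mg. Under section 7.3 the dose rises only after 2 weeks without reaching 50,000/µL, stays as it is at 50,000 to <100,000/µL, and is stopped at 100,000/µL or more. Section 7.3 has no rule for restarting the drug after that stop.

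**The concern.** A response scale should place every treated patient in one category. Here the bottom category needs twice as much drug as the protocol permits, and the middle category carries a dose condition that the titration scheme does not allow. Whoever tabulates response will have to supply the missing rules. If they do so after seeing the platelet counts, the classification is no longer prespecified.

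Section 12.0 says that categorical data will be reported as counts and percentages, so the likely symptom is a table with no non-responders, or one whose denominator has lost patients. Section 9.2 plans to correlate laboratory results with whether a response occurred, and secondary endpoint 4 in section 10.2 describes platelet response by AML subtype, etiology and cytogenetic risk. Neither says which definition of response applies. If they rely on section 10.1.2, the absent-response group has no members as written.

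**Working it through.** **Duration.** Required for no response (section 10.1.2): 8 × 7 = 56 days of eltrombopag. Permitted (section 7.7; section 8.4, note a): 4 × 7 = 28 days from the first dose. Since 28 < 56, no course given per protocol meets the condition.

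**Time at the highest dose.** Escalation comes after 2 weeks at the earliest (section 7.3), so at most 28 − 14 = 14 days, or 14/28 = 50% of the longest course, are at the highest dose. The partial-response wording, read literally, asks for 100%.

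**Readings that might rescue the 8 weeks.**

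- *Four weeks of drug plus four of follow-up.* The wording is 8 weeks of therapy. Sections 7.8 and 8.2 (item 9) specify the 4-week response follow-up for patients who reached 100,000/µL, who are not the candidates for no response.
- *Resumed drug lengthens the course.* Resumption appears only in the partial-response text, after a complete response, and section 7.7 counts from the first dose.
- *Interruptions lengthen the course.* Section 7.6 says missed doses are not replaced.

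**Would changing only 8 to 4 be enough?** Five kinds of course, classified as written and then with that single change:

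1. *Escalated, below 50,000/µL for all 4 weeks.* As written: no category. With 4: no response.
2. *Stopped early below 50,000/µL and not replaced* (section 7.6 does not replace patients removed after a 1-week interruption for adverse effects). As written: no category. With 4: still none, because the 4 weeks were not completed.
3. *Kept on the starting dose at 50,000 to <100,000/µL.* Partial response only if 'highest dose' means the highest dose assigned to that patient. Otherwise no category, before or after the change, because the patient never received the maximal escalated dose.
4. *Escalated, reaching 50,000 to <100,000/µL, full course.* On the literal dose reading: no category as written, and no response with 4, despite having reached 50,000/µL. If the dose condition is met by having reached the maximum: partial response.
5. *Reached 100,000/µL, stopped, fell within 4 weeks, with neither resumption nor post-remission therapy.* Durability fails, so not complete response. If the resumption parenthesis is a condition, not partial response either. With 4, it becomes no response only if the patient had also completed 4 weeks and received the maximal dose. If the parenthesis is merely descriptive, it can be read as partial response.

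These are illustrations of how the text behaves. They are neither a complete list of possible courses nor patient frequencies.

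**The case against.** The best case on the other side is about reach. No objective, secondary endpoint or statistical paragraph names complete, partial or no-response rates. The primary endpoint (section 10.1.1) and the two-stage rule in section 12.0 rest on at least 50,000/µL by day 24, which does not use this scale. That stands. A reader who infers that the trial's main conclusion, its stopping rule or its sample size is compromised goes beyond the documents.

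A second objection concerns patients who fall below 100,000/µL soon after stopping. One might infer that they can never be classified. The text does not support that. The parenthesis "necessitating resumption of eltrombopag treatment" can be read as an expected consequence and not a requirement, and complete response is dated to the "first day of the four-week period with platelet count greater than" 100,000/µL, so an early fall might be taken as a fall after complete response. Some such patients would also become no response once 8 is changed to 4. What stands is that their category depends on a reading the protocol does not state.

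A third objection is that any tally of unclassified courses reflects how the courses were listed and which readings were allowed. That is correct, so none is offered here.

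Finally, section 12.0 plans on eligible and evaluable patients, so early stoppers might be meant to drop out as not evaluable. The documents do not define evaluable for this scale, so that too would be a rule added later. Section 1.2.3 mentions an 8-week treatment period in another eltrombopag study. It is tempting to infer that the figure was carried over from there, but the documents do not show it.

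**Conclusion.** The definition is wrong as written. No response needs 56 days of drug against 28 allowed, so no patient treated per protocol can be scored as such. The first partial-response route is likewise unreachable on its literal wording (at most 14 of 28 days at the highest dose). The first conclusion needs only the current text of sections 7.7, 8.4 and 10.1.2. The second also uses sections 7.1 to 7.3 and holds only for the literal reading. Correcting the number alone leaves at least the early stoppers below 50,000/µL without a category.

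The documents do not say how many patients would be affected, and no figure is claimed. For scale, if all 31 patients formed the denominator, each one reassigned would move a reported rate by 1/31 = 3.2 percentage points. The consequence is limited to the section 10.1.2 scale, and to section 9.2 and secondary endpoint 4 if they use it.

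**What to change.** 1. Reconcile the 8-week condition in section 10.1.2 with the 4-week course in sections 7.7 and 8.4, and the highest-dose and resumption wording in section 10.1.2 with section 7.3. Which duration or dose rule should prevail is for the investigators; none is proposed here.
2. Before the platelet data are analysed, restate the three categories so that every dosed, non-replaced patient falls in exactly one. Early stoppers below 50,000/µL should either count as no response or appear as a prespecified not-evaluable group kept in the denominator. Give an explicit rule for a fall below 100,000/µL within 4 weeks of stopping.
3. State in section 9.2 and in secondary endpoint 4 whether response means these categories or the endpoint of at least 50,000/µL.
4. The 4-week durability check needs counts after 100,000/µL is reached. Section 6.4 makes outpatient counts weekly for 4 weeks after stopping, section 8.2 (item 9) says standard of care over that period, and note h in section 8.4 leaves them to the physician's discretion. These three passages must be reconciled.

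The cost is wording only. No extra patients are needed, and the categories rest on platelet counts and transfusion dates that the protocol already collects, subject to item 4.
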